Study Title: A Pilot Study in Feasibility and Safety: Point of Care testing with thromboelastography (TEG) for blood product transfusion and coagulation in patient's requiring extracorporeal membrane oxygenation (ECMO)

Principal Investigator: [name], MBA

Document: Study Protocol
Document Date: 29 AUG 2019

NCT #: NCT02887820
STUDY #: STUDY19070239

Basic Study Information

1. * Title of study:

A Pilot Study in Feasibility and Safety of Point of care testing with thromboelastography (TEG) for blood product transfusion and anticoagulation in patients requiring Extracorporeal Membrane Oxygenation (ECMO)

2. * Short title:

Evaluate the feasibility of following TEG algorithm in patients requiring ECMO

3. * Brief description:

This is a pilot study that seeks to evaluate the feasibility and safety of using a TEG algorithm in addition to traditional laboratory tests to guide transfusion and anticoagulation management of ECMO patients. Patients requiring ECMO exhibit a high risk of mortality due to bleeding and thrombosis, as the non-biological surface of the extracorporeal surface activates both procoagulant and anticoagulant mechanisms (1). Using TEG as a point-of-care device to provide individualized, goal-directed therapy in this population may help decrease blood product transfusion and lead to improved blood management overall.

All adult patients requiring ECMO will be considered for the trial, with a target enrollment of 50 participants over a two-year period. For each enrolled participant, a TEG transfusion algorithm will be followed for patients exhibiting inadequate hemostasis in the operating room (Flowchart 1), and then a second TEG algorithm will be followed in the ICU when hemostasis is normal and heparin is introduced (Flowchart 2). Statistical analysis of the feasibility and compliance of using a TEG algorithm will determine the likelihood of exploring future clinical trials involving TEG-driven coagulation and transfusion management of the ECMO population.

4. * What kind of study is this?

Single-site study

5. * Will an external IRB act as the IRB of record for this study?

Yes No

6. * Local principal investigator:

[name]

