2. * Describe the relevant prior experience and gaps in current knowledge including preliminary data. Provide for the scientific or scholarly background for, rationale for, and significance of the research based on existing literature and how it will add to existing knowledge:

A study by Shore-Lesserson, et al in 1999 demonstrated that in patients undergoing cardiac surgery, use of a TEG based transfusion algorithm resulted in less transfusions than a more traditional algorithm based on ACT, platelet count, prothrombin time (PT), and PTT. This result was hypothesized to be due to TEG's ability to provide qualitative assessment of factor and platelet function, rather than solely quantitative results (Shore et al). Another recent study by Weber, et al. demonstrated that the use of rotational thromboelastometry (ROTEM) to guide hemostatic component therapies was superior to laboratory coagulation testing in terms of efficacy and cost (Weber et al). It has been shown that use of ROTEM and TEG is associated with less perioperative blood loss without increases in transfusions or mortality (Tanaka et al).

A retrospective analysis of 578 patients requiring veno-venous (VV) or VA-ECMO over the past nine year period at the University of Pittsburgh Medical Center was accomplished. Data included duration of ECMO, blood products transfused, and complications from ECMO. The data collected also detailed the transfusion of total blood products and packed red blood cells for patients on VV and VA ECMO. VA ECMO appears to be associated with the greatest amount of transfusion, especially on the day of initiation. Furthermore, in reviewing the data, it appears that the patients who required VA ECMO had a surgery, generally cardiotomy, prior to institution of VA ECMO. Resultantly, in many cases, the transfusion of blood products is generally associated with the day of the primary surgery. This preliminary

data is very important in that it is a guide for the investigators in the determination of where the greatest impact can be made in terms of reducing blood transfusion in the operative setting. Because of this data, patients s/p surgery (usually cardiotomy) appear to have higher incidence of transfusion and as a result, a protocolized and algorithmic focus is expected to yield a reduction of blood products in this patient population.

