While the use of protocol driven use of TEG in CPB has been described, few studies have investigated the utility of TEG on the direction of patient care during ECMO for adult patients. We know that Point-of-care coagulation testing allows for rapid assessment and goal directed therapy. ROTEM and TEG allow for particularly rapid results by providing a picture of global coagulation status in around 20 minutes. This allows for more appropriate and timely transfusion of various blood products, including red blood cells, platelets, plasma, cryoprecipitate, and clotting factors (Tanaka et al). We believe the application of algorithmic use of TEG to management of hemostasis and anticoagulation for patients on ECMO is novel and has the potential to have a major impact on patient care.

Study Design

1. Total number of subjects to be enrolled at this site (enter -1 for chart reviews, banking, registries):

100

2. Describe and explain the study design:

The proposed study design is single center, prospective, pilot clinical trial

3. Describe the primary and secondary study endpoints:

Primary outcome variable- Determine the feasibility of following the protocol for this trial of TEG for ECMO.

Secondary outcome variable- Assess clinical outcomes including the rates of transfusion, major bleeding, and major complications in patients on ECMO managed with TEG in addition to traditional laboratory measures of coagulation.

4. Provide a description of the following study timelines:

Duration of an individual subject's active participation:

30 days

Duration anticipated to enroll all subjects:

1 year

Estimated date for the investigator to complete this study (complete primary analyses):

12/1/2020

5. List the inclusion criteria:

Adult patient requiring ECMO

6. List the exclusion criteria:

Children less than 18 years of age

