*** Identify the subgroups and provide a justification:**

Children less than 18 years of age as only adults are seen at this institution

8. Describe the power analysis used and cite your method of statistical analysis.

If a power analysis is not possible, thoroughly justify the sample size required for the study, including appropriate literature citation (alternatively provide page reference in attached protocol):

Approximately 100 ECMO cases are seen per year in the UPMC Presbyterian

Hospital, of which, approximately 50% require VA-ECMO. We expect to enroll 50-60% of those patients per year. Regarding Specific Aim 1: Feasibility will be defined by a minimum of 80% of patients who will have followed the algorithm on greater than or equal to 90% of the days on ECMO. The data obtained from this pilot and feasibility study will help to establish event rates, transfusion rates and volumes, to inform subsequent larger clinical trials. Incidence of protocol compliance will be analyzed by Chi Square test or Fisher exact test. P value less than 0.05 will be considered significant. Transfusion rates and volumes as well as clinical outcome rates will be analyzed by independent-sample t test or Mann Whitney U test wherever appropriate.

Cognitively Impaired Adults

1. * Provide a justification for the inclusion of adult subjects who are unable to provide direct consent for study participation:

A large proportion of patients will undergo ECMO in an emergent setting, in which they themselves are unable to provide consent due to their clinical status. Once it is determined by an investigator that the patient is unable to provide consent, consent will be obtained from the patient's proxy.

2. * Specify the criteria used to determine that a given potential adult subject is not able to provide direct consent for participation and identify who will responsible for that determination:

If a patient is heavily sedated, unconscious or intubated they will not be able to provide consent and a investigator will make the determination to approach the Proxy for consent.

Research Activities

1. *** Provide a detailed description of all research activities (including screening and follow-up procedures) that will be performed for the purpose of this research study. This description of activities should be complete and of sufficient detail to permit an assessment of associated risks.**

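### The protocol gives two sample sizes and two enrolment periods for one single-site study (50 over two years, 100 in one year), and its accrual forecast does not settle which is meant

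*Combined protocol and SAP*

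**What the plan says.** Three places in the protocol bear on the size and duration of enrolment.

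- **Basic Study Information, item 3 (brief description):** "All adult patients requiring ECMO will be considered for the trial, with a target enrollment of 50 participants over a two-year period". Item 4 of the same section describes a single-site study, so a site total and a study total are the same number.
- **Study Design, items 1 and 4:** under "Total number of subjects to be enrolled at this site" the entry is 100. Under "Duration anticipated to enroll all subjects" the entry is 1 year. The date for completing the primary analyses is entered as 12/1/2020.
- **Study Design, item 8 (power analysis or sample-size justification):** the annual caseload is given first: "Approximately 100 ECMO cases are seen per year in the UPMC Presbyterian". For the VA share and the fraction expected to enrol, the item then has: "of which, approximately 50% require VA-ECMO. We expect to enroll 50-60% of those patients per year". Next it sets the success criterion, "Feasibility will be defined by a minimum of 80% of patients" following the algorithm on at least 90% of ECMO days. It states no target N, power or precision.

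Study Scope item 10 carries an identifier from an earlier IRB system and an attached continuing review form. This fits the transfer of a study that was already approved. The form's content is not shown, and no number already enrolled appears in the visible text.

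**The concern.** The total differs by a factor of two and the enrolment period differs by a factor of two in the opposite direction. The implied enrolment rates are therefore 50/2 = 25 a year and 100/1 = 100 a year, a fourfold difference. All of this is current text, not a record of superseded wording.

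At stake is whether a reader can tell when enrolment is complete, and how precisely the primary feasibility proportion will be estimated. Item 8 also says the pilot will establish event and transfusion rates for later trials, and the precision of those estimates depends on the same N. Item 8 is where one would look to settle the matter, but it contains only an accrual forecast, and the group to which the 50-60% applies can be read in two ways.

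**Working it through.** **Inputs.** From Study Design item 8: about 100 ECMO cases a year, a VA share of about 50%, and an enrolled fraction of 50-60%. From the brief description: 50 in 2 years. From Study Design items 1 and 4: 100 in 1 year.

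**Accrual per year** = cases per year × share of cases in the base × enrolled fraction.

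- Base is VA-ECMO: 100 × 0.5 × (0.50 to 0.60) = 25 to 30 a year.
- Base is all ECMO: 100 × (0.50 to 0.60) = 50 to 60 a year.

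**Reproducing the stated figures.** On the VA reading, 25 × 2 = 50 matches the brief description, using the lower end of the range. On the all-ECMO reading, 50 × 2 = 100 matches the N in Study Design item 1, but over the two years of the brief description; 50 × 1 = 50 matches the N of the brief description, but over the one year of item 4.

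| | VA-ECMO base | All-ECMO base |
|---|---|---|
| Enrolled in 1 year | 25-30 | 50-60 |
| Enrolled in 2 years | 50-60 | 100-120 |
| Years to reach 50 | 50/30 to 50/25 = 1.7-2.0 | 50/60 to 50/50 = 0.8-1.0 |
| Years to reach 100 | 100/30 to 100/25 = 3.3-4.0 | 100/60 to 100/50 = 1.7-2.0 |

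**100 in one year.** Starting from zero, this would need 100/100 = 100% of all ECMO cases, or 100/50 = 200% of VA cases, against 50-60% forecast. If the one year is only the time remaining, the number already enrolled would have to be:

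- VA base: 100 − 30 = 70 to 100 − 25 = 75.
- All-ECMO base: 100 − 60 = 40 to 100 − 50 = 50.

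**Precision at each N.** For x patients meeting the criterion out of n, the exact (Clopper-Pearson) 95% limits are the 0.025 quantile of Beta(x, n − x + 1) and the 0.975 quantile of Beta(x + 1, n − x). At an observed 80%:

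- n = 50, x = 40: 66.3% to 90.0%, a width of 23.7 points.
- n = 100, x = 80: 70.8% to 87.3%, a width of 16.5 points.

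**The case against.** The strongest reply is that the study was already running. If some patients were enrolled under the earlier record, the one year in Study Design may mean time remaining. That section's dates are coherent: 29 August 2019 plus one year plus 30 days of participation falls in late September 2020, before 12/1/2020. This stands as a possible explanation. A reader might infer from the accrual figures that 100 in one year is simply unattainable; the documents do not support that, because it holds only for a start from zero. However, the item asks for the time to enrol all subjects, no earlier enrolment is stated, and carry-over does not explain why the brief description targets 50 over two years.

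A reader might also infer that the VA reading is the right one, that 50 over two years is therefore the intended plan, and that the Study Design entries are the mistake. VA-ECMO is the nearest antecedent in item 8, and the background says "VA ECMO appears to be associated with the greatest amount of transfusion, especially on the day of initiation". Yet the background goes on to name patients after surgery as the focus, the sole inclusion criterion is any adult requiring ECMO, and the data list records whether ECMO is VV or VA (printed as AV). On the all-ECMO reading, 100 fits a two-year period. The forecast does not decide between the two totals.

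Two further inferences should be resisted. One is that the two-year period overruns the completion date: the documents do not say when the two years began. The other is that the primary endpoint fails: the 80% rule can be computed at any N.

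**Conclusion.** The contradiction stands as written: 50 over two years against 100 in one year, for one site, with nothing visible to reconcile them. It should be corrected, but its consequence is limited. It leaves the end of enrolment undefined and the 95% interval for feasibility uncertain between about 24 and 16.5 points wide at 80% observed, a modest difference.

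The accrual results take the approximate caseload and percentages in item 8 at face value. The interval widths assume that every enrolled patient counts in the feasibility proportion. Which N is intended cannot be determined from the documents, and the shortfall against 100 in one year is conditional on how many patients, if any, were carried over.

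**What to change.** - State one N and one enrolment period, identically in the brief description and in Study Design items 1 and 4, with a completion date that follows from them.
- In Study Design item 8, say whether the 50-60% applies to VA-ECMO or to all adult ECMO patients. This clarifies a forecast; eligibility need not change.
- State how many patients enrolled under the earlier IRB record, if any, count toward N.
- Give the expected exact 95% interval for the feasibility proportion at the chosen N, as in the calculation above.

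The choice of N belongs to the investigator. The cost is a few text edits and, for some combinations of N and accrual base, a later completion date. No procedure is added for any patient.

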<div[]([[{"id": 3, "text": "3. Have you, [name], verified that all members of the research team have the appropriate expertise, credentials, training, and if applicable, child clearances and/or hospital privileges to perform those research procedures that are their responsibility as outlined in the IRB application?"}]]

<div[]([[{"label": "Yes", "value": 1}, {"label": "No", "value": 0}], [{"label": "Yes", "value": 1}, {"label": "No", "value": 0}]]

Study Scope

Check all that apply

1. * Will this study actively recruit any of the following populations?

- Adults with impaired decision-making capacity
- Children (under the applicable law of the jurisdiction in which the research will be conducted (<18 years for PA))
- Children who are Wards of the State
- Employees of the University of Pittsburgh/UPMC
- Medical Students of University of Pittsburgh as primary research group
- Students of the University of Pittsburgh
- Neonates of uncertain viability
- Non-viable neonates
- Non-English speakers
- Nursing home patients in the state of Pennsylvania
- Pregnant women
- Prisoners
- N/A

2. * Will any Waivers be requested?

- Waiver/Alteration of Consent
- Waiver to Document Consent
- Waiver/Alteration of HIPAA
- Exception from consent for emergency research
- N/A

3. * Will this study involve any of the following?

- Specimens
- Honest Broker to provide data/specimens
- Return of Results to Subjects or Others
- Fetal tissue
- N/A

4. * Will Protected Health Information be collected?

- Pitt medical records
- UPMC medical records
- Other Institutions' medical records
- N/A

5. * Other Requests?

- Deception (if not Exempt, also requires Waiver/Alteration of Consent)
- Emergency Use / Single Patient Expanded Access (using FDA Form 3926)

- Placebo Arm
- Withdraw from usual care
- N/A

6. * Determining Scientific Review:

Department Scientific Review (this option MUST be picked if there is DoD funding)

*** Choose the appropriate organization to conduct the scientific review:**

U of Pgh | School of Medicine | Anesthesiology

7. * Has this study (or substantially similar study) been previously disapproved by the Pitt IRB or, to your knowledge, by any other IRB?

Yes No

Review the [HRPO policy](#), if participating in research at the VA Pittsburgh Healthcare System or using funding from the VA

8. * Does the study use an approved drug or biologic, use an unapproved drug or biologic, or use a food or dietary supplement to prevent, diagnose, cure, treat, or mitigate a disease or condition?

Yes No

9. * Does the study evaluate the safety or effectiveness of a device (includes in-vitro laboratory assays)?

Yes No

10. * Is this application being submitted to convert an approved study from OSIRIS to PittPRO? ([Tip Sheet](#))

Yes No

Download the [OSIRIS Transition Continuing Review form](#), complete and upload below. If you need to attach any additional documents (e.g., data and safety monitoring reports), upload in the Local Supporting Documents page and note the Renewal on the form. **Exempt** submissions in OSIRIS also need to move into PittPRO if they remain ongoing. These will not be considered transitions but new studies. Therefore, Study Scope #10 will be answered as "No." Once the new exempt determination has been issued, the OSIRIS application can be closed. Any exempt submission remaining in OSIRIS by the end of August 2020 will be closed by our office. Please use the "Add Comment" to provide the OSIRIS study number.

OSIRIS Transition Continuing Review form:

[Continuing Review Form 2019\(0.03\)](#)

*** OSIRIS ID**

PRO16060542

11. * Does your research protocol involve the evaluation or use of procedures that emit ionizing radiation and, after reviewing this [HUSC guidance](#), does your research protocol require HUSC review? (If yes, upload the [HUSC form](#) in the Local Supporting Documents section). If you are unsure of review

requirement, select yes.

Yes No

Research Sites

1. Choose all sites that apply:

UPMC

* Select the UPMC sites where research will be conducted:

Presbyterian

2. Describe the availability of resources and the adequacy of the facilities to

conduct this study:

UPMC Presbyterian is a hospital with an Acute Interventional Perioperative Pain Service (AIPPS). The anesthesiologists here routinely participate in clinical trials and various other types of clinical research, are well acclimated to conducting clinical research with respect to good clinical practice. There are sufficient resources of manpower and supplies to conduct the study

Click **Continue** as this page was intentionally left blank.

Recruitment Methods

*** Will you be recruiting individuals for participation in this study?**

Yes No

1. * Describe who will be recruiting individuals for participation for this study:

The principal investigator or co-investigator will approach patient with the assistance of research associates or coordinators if they are conscious and obtain consent.

2. * Select all methods to be used for recruitment:

Directly approaching potential subjects (in-person)

3. * Provide details on your recruitment methods:

Patient will be identified through medical records and operative schedules to determine study eligibility. The principal investigator or co-investigator will approach patient with the assistance of research associates or coordinators if they are conscious and obtain consent. A proxy consent will be obtained in patients who are unable to provide consent.

4. * Describe all compensation/incentives offered to participants and timing of these offers:

Patients are not compensated for this study.

5. Recruitment materials: (attach all material to be seen or heard by subjects, including advertisements and scripts)

Document Category Date Modified Document History

There are no items to display

Study Aims

1. * Describe the purpose, specific aims, or objectives and state the hypotheses to be tested:

Specific Aim: A pilot study to evaluate the feasibility and safety of a research protocol, to evaluate the use of thromboelastography (TEG) in post cardiotomy, thoraco-abdominal, and trauma surgical patients requiring extracorporeal membrane oxygenation (ECMO). It is expected that these data will inform a large-scale clinical trial design. The safety of the TEG protocol will be based upon the amount of bleeding and thrombotic events.

a. To determine the feasibility and adherence rates of following the protocol for this trial of TEG for ECMO, and identify potential interventions to improve adherence. This does not mean that the clinicians are subjects, as the clinicians are already well-practiced in interpreting TEG as a measure of coagulation and will be using TEG as a supplement to conventional testing as per study protocol. Further, all clinicians will follow the same TEG protocol for every patient enrolled in the trial.

The feasibility and safety will be assessed by the number of transfusions that follow the TEG algorithm, how many patients complete the study, number of TEGs done, missing or extra TEGs, and number of re-operative events

2. * Describe the relevant prior experience and gaps in current knowledge including preliminary data. Provide for the scientific or scholarly background for, rationale for, and significance of the research based on existing literature and how it will add to existing knowledge:

A study by Shore-Lesserson, et al in 1999 demonstrated that in patients undergoing cardiac surgery, use of a TEG based transfusion algorithm resulted in less transfusions than a more traditional algorithm based on ACT, platelet count, prothrombin time (PT), and PTT. This result was hypothesized to be due to TEG's ability to provide qualitative assessment of factor and platelet function, rather than solely quantitative results (Shore et al). Another recent study by Weber, et al. demonstrated that the use of rotational thromboelastometry (ROTEM) to guide hemostatic component therapies was superior to laboratory coagulation testing in terms of efficacy and cost (Weber et al). It has been shown that use of ROTEM and TEG is associated with less perioperative blood loss without increases in transfusions or mortality (Tanaka et al).

A retrospective analysis of 578 patients requiring veno-venous (VV) or VA-ECMO over the past nine year period at the University of Pittsburgh Medical Center was accomplished. Data included duration of ECMO, blood products transfused, and complications from ECMO. The data collected also detailed the transfusion of total blood products and packed red blood cells for patients on VV and VA ECMO. VA ECMO appears to be associated with the greatest amount of transfusion, especially on the day of initiation. Furthermore, in reviewing the data, it appears that the patients who required VA ECMO had a surgery, generally cardiotomy, prior to institution of VA ECMO. Resultantly, in many cases, the transfusion of blood products is generally associated with the day of the primary surgery. This preliminary

data is very important in that it is a guide for the investigators in the determination of where the greatest impact can be made in terms of reducing blood transfusion in the operative setting. Because of this data, patients s/p surgery (usually cardiotomy) appear to have higher incidence of transfusion and as a result, a protocolized and algorithmic focus is expected to yield a reduction of blood products in this patient population.

While the use of protocol driven use of TEG in CPB has been described, few studies have investigated the utility of TEG on the direction of patient care during ECMO for adult patients. We know that Point-of-care coagulation testing allows for rapid assessment and goal directed therapy. ROTEM and TEG allow for particularly rapid results by providing a picture of global coagulation status in around 20 minutes. This allows for more appropriate and timely transfusion of various blood products, including red blood cells, platelets, plasma, cryoprecipitate, and clotting factors (Tanaka et al). We believe the application of algorithmic use of TEG to management of hemostasis and anticoagulation for patients on ECMO is novel and has the potential to have a major impact on patient care.

Study Design

1. Total number of subjects to be enrolled at this site (enter -1 for chart reviews, banking, registries):

100

2. Describe and explain the study design:

The proposed study design is single center, prospective, pilot clinical trial

3. Describe the primary and secondary study endpoints:

Primary outcome variable- Determine the feasibility of following the protocol for this trial of TEG for ECMO.

Secondary outcome variable- Assess clinical outcomes including the rates of transfusion, major bleeding, and major complications in patients on ECMO managed with TEG in addition to traditional laboratory measures of coagulation.

4. Provide a description of the following study timelines:

Duration of an individual subject's active participation:

30 days

Duration anticipated to enroll all subjects:

1 year

Estimated date for the investigator to complete this study (complete primary analyses):

12/1/2020

5. List the inclusion criteria:

Adult patient requiring ECMO

6. List the exclusion criteria:

Children less than 18 years of age

7. Will children or any gender, racial or ethnic subgroups be explicitly excluded from participation?

Yes No

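### The measures listed for safety include no thrombotic event, and the tests assigned to clinical outcome rates need a comparison group that the plan does not describe

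*Combined protocol and SAP*

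**What the plan says.** **Aim.** Study Aims, item 1, puts safety beside feasibility in the specific aim and states its basis: "The safety of the TEG protocol will be based upon the amount of bleeding and thrombotic events".

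**Measures.** The same item closes with how both will be judged: "The feasibility and safety will be assessed by the number of transfusions that follow the TEG algorithm, how many patients complete the study", continuing with "number of TEGs done, missing or extra TEGs, and number of re-operative events".

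**Secondary endpoint.** Study Design, item 3: "Assess clinical outcomes including the rates of transfusion, major bleeding, and major complications in patients on ECMO managed with TEG". Thrombosis is not named, and major complications are not defined.

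**Analysis.** Study Design, item 8, gives feasibility a numeric bar: "Feasibility will be defined by a minimum of 80% of patients who will have followed the algorithm" on at least 90% of ECMO days. For the clinical results it says: "Transfusion rates and volumes as well as clinical outcome rates will be analyzed by independent-sample t test or Mann Whitney U test". Study Design, item 2, describes a single-center prospective pilot and mentions no second group.

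**Data.** Research Activities, item 1, records clinical thrombotic or hemorrhagic events, clots in the circuit or oxygenator, pump and oxygenator exchanges, surgery for hemorrhage, and chest tube output with blood loss. Medical Records, item 1, repeats these.

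**Safeguards.** Every row of the heparin nomogram lets anti-Xa prevail when it and TEG disagree. Risk and Benefits, item 2, says that standard tests lead coagulation management. Data Safety and Monitoring, item 1, has the investigators review adverse events monthly or quarterly, with power to change or stop the study.

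**The concern.** The plan states what safety rests on and then lists measures that mostly record something else. Adherence and completion counts say whether the algorithm was followed, not whether patients bled or clotted. Re-operation captures only bleeding or clotting that led back to surgery.

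The algorithm combines transfusion triggers with anticoagulation targets, so harm could run in either direction. A report that follows the listed measures literally could describe safety without a single thrombotic count. The tests named for clinical outcome rates would not fill the gap, because they compare two samples and the plan describes one.

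What is at stake is the pilot's ability to answer its second aim in a form that a later trial team can use: how many patients had a thrombotic event, how many bled, and how precisely those rates are known.

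**Working it through.** The plan states no safety figure, so there is none to reproduce. The check is a comparison of texts, followed by the precision that the proposed reporting would give.

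**Step 1. Classify the five measures in Study Aims, item 1.**

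- Transfusions that follow the algorithm: adherence
- Patients who complete: completion
- TEGs done: adherence
- Missing or extra TEGs: adherence
- Re-operative events: clinical, a partial marker of bleeding

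Result: 4 of 5 are adherence or completion counts, 1 of 5 is clinical, and 0 of 5 is thrombotic.

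**Step 2. Compare the recorded data with that list.**

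| Bleeding or clotting item in Research Activities, item 1 | Counterpart in the Study Aims list |
|---|---|
| Chest tube output and blood loss | none |
| Pump exchange | none |
| Oxygenator exchange | none |
| Circuit or oxygenator clot without exchange | none |
| Surgery for hemorrhage | re-operative events |
| Clinical thrombotic or hemorrhagic event | none |

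Result: 1 of 6. A patient with a stroke who is not re-operated is recorded in the data but adds nothing to the one clinical measure in the list. Under Study Design, item 3, that patient counts only if the undefined major complications are taken to include stroke.

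**Step 3. Check the test against the design.** An independent-sample t test uses (mean of group 1 − mean of group 2) / standard error of the difference. The Mann-Whitney U test ranks the observations of two groups together. With one group neither statistic exists. In addition, whether a patient had an event is a yes/no outcome, for which a proportion with its interval is the natural summary.

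**Step 4. Precision with n/N and an exact interval.** Clopper-Pearson, for x patients with an event out of n:

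- lower limit = Beta quantile at 0.025 with parameters x and n − x + 1
- upper limit = Beta quantile at 0.975 with parameters x + 1 and n − x

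The sample size is 50 in Basic Study Information, item 3, and 100 in Study Design, item 1, so both are shown. The documents give no event rate; 10%, 20% and 30% are assumed for illustration.

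| Assumed observed rate | n = 50 | n = 100 |
|---|---|---|
| 10% | 5/50: 3.3% to 21.8% | 10/100: 4.9% to 17.6% |
| 20% | 10/50: 10.0% to 33.7% | 20/100: 12.7% to 29.2% |
| 30% | 15/50: 17.9% to 44.6% | 30/100: 21.2% to 40.0% |

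With no events, the upper limit is 1 − 0.025^(1/n): 7.1% at 50 and 3.6% at 100.

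**Step 5. The bivalirudin subset.** Research Activities, item 1, says that the TEG transfusion parameters do not apply to patients on bivalirudin. The documents do not say how many that will be. If, as an assumption, 30 patients were managed without it, 3/30 would give 2.1% to 26.5%.

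**The case against.** **The safety basis is already stated.** The sentence on bleeding and thrombotic events names the safety measure. The five-item list follows a sub-aim on feasibility and adherence, and nothing says that it replaces that sentence. This stands in part: it makes the problem a mismatch in drafting rather than an omitted outcome. But the list claims to assess safety as well, and neither the secondary endpoint nor the analysis text restores thrombosis.

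**TEG rarely acts alone.** Anti-Xa overrides TEG for heparin. Plasma and cryoprecipitate require signs of bleeding plus both a TEG and a conventional abnormality, and the red-cell trigger uses no TEG value. Only the platelet trigger lets a TEG value start a transfusion by itself. This stands and limits the risk to patients. It does not say how safety will be summarised.

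**A pilot need not test safety formally.** Agreed. Estimation with an interval is enough, and no hypothesis test is asked for.

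**The two-sample tests could serve subgroup comparisons, such as VV against VA ECMO.** They could, but the plan names no such comparison, and it would describe differences between subgroups rather than the overall event rate.

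**A stronger reading.** From "Statistical analysis of the feasibility and compliance of using a TEG algorithm will determine the likelihood of exploring future clinical trials" a reader might infer that the pilot would lead to a larger trial whatever the number of bleeding or thrombotic events. The documents do not support that. The sentence belongs to a brief description and speaks of likelihood, not of a go/no-go rule. Study Design, item 8, says that event rates will inform later trials, and the investigators can stop the study on adverse events.

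**Conclusion.** The concern holds as a mismatch between the safety aim and the measures and analysis meant to deliver it. Its size is textual: no thrombotic event among five listed measures, one of six recorded bleeding or clotting items represented, and a test family that cannot be computed on the single group described. Patients are monitored and the needed data are collected, so the consequence falls on what the pilot can report.

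Two further inferences should be resisted. A reader might conclude that thrombotic events are not captured; the list of recorded parameters shows that they are. A reader might also conclude that the plan must fix an unacceptable event rate from the 578-patient in-house series. Of that series the protocol says only "Data included duration of ECMO, blood products transfused, and complications from ECMO". It does not say that thrombotic events can be separated out, and a pilot that estimates rates does not need such a threshold.

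The verdict assumes that Flowcharts 1 and 2, which are not shown, contain no safety definitions; the protocol describes them as transfusion algorithms. The intervals rest on the assumed rates and the two stated sample sizes.

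**What to change.** 1. **Study Aims, item 1.** Keep the adherence and completion items for feasibility. For safety, name two measures: patients with at least one thrombotic event and patients with at least one bleeding event, both built from the items in Research Activities, item 1. Show circuit or oxygenator clots and exchanges separately.
2. **Study Design, item 3.** Name thrombosis beside major bleeding.
3. **Study Design, item 8.** For these event rates, replace the two-sample tests with n/N and exact 95% confidence intervals. Show them for all patients and again for patients managed without bivalirudin.
4. **Study Design, item 8.** State that safety is descriptive and will be reported beside the feasibility bar (0.80 × 50 = 40 patients, or 0.80 × 100 = 80) when a larger trial is considered.

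The cost is a few sentences and one more table. The event items are already on the list of recorded data. The drawback is that the intervals will be wide, and wider still in the subset without bivalirudin.
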